#### [Discontinuation criteria](#)

- Suicidality according to C-SSRS with a positive score to question 4 or 5 or upon the investigator's discretion.
- Severe somatic illness, as judged by the investigator.
- The patient wishes to stop participation and/or withdraws consent.
- The patient is unable to follow the treatment in one of the arms.
- Treatment will be terminated if the subject does not show up for two virtual meetings with the study staff or two meetings with the GP/psychologist, without cancelling, and

the study personnel are unable to get in contact with the participant. Attempts of contact are documented in the CRF.

### [Withdrawal and dropout](#)

Withdrawal from the study will occur at the time when any of the discontinuation criterion are fulfilled, as judged by the investigator.

If possible, data regarding all outcome measures will be collected immediately or as soon as possible after the time of withdrawal. The primary outcome measure (HAM-D6) will have the highest priority. The primary reason for discontinuation will be recorded as well as the time of discontinuation. Subjects who have withdrawn will not be replaced.

If a study participant wishes to dropout, an interview regarding the reasons for dropping out will be offered to the patient concerned. The planned next rating session will be executed as soon as possible hereafter.

It is recommended that study participants discuss further treatment with the treating general practitioner responsible for their care.

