## Measures and Outcomes

### Modified intention-to-treat (mITT) population and Per Protocol (PP) populations

The modified intention-to-Treat (mITT) population encompasses all randomised participants with at least one post-baseline HAM-D6 rating. The endpoint of the study is 12 weeks.

For participants with premature endpoints, the latest endpoint available will be used with last-observation-carried-forward (LOCF).

The Per Protocol (PP) populations are defined as completers at week 4 (PP4), at week 8 (PP8), or at week 12 (PP12).

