### Primary outcome

The primary outcome of the study is the difference in HAM-D6 score from baseline to end of study at 12 weeks. It will be based on the mITT population.

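### Every discontinuation criterion ends study follow-up, so some patients who could still be rated have no week-12 HAM-D6 by rule and enter the primary analysis with a carried-forward value or not at all

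*Protocol*

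**What the plan says.** The protocol section on withdrawal and dropout sets the rule: "Withdrawal from the study will occur at the time when any of the discontinuation criterion are fulfilled, as judged by the investigator". The criteria stand in the section before it. They include "Suicidality according to C-SSRS with a positive score to question 4 or 5 or upon the investigator's discretion", severe somatic illness as the investigator judges it, the patient's own wish to stop, and "The patient is unable to follow the treatment in one of the arms". The criterion on missed appointments is worded as an end of treatment ("Treatment will be terminated if the subject does not show up for two virtual meetings with the study staff or two meetings with the GP/psychologist"), and it also requires that staff cannot reach the patient.

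After withdrawal, the protocol asks for one assessment: "If possible, data regarding all outcome measures will be collected immediately or as soon as possible after the time of withdrawal". HAM-D6 has first priority there. For a patient who wishes to drop out, "The planned next rating session will be executed as soon as possible hereafter". No section keeps a withdrawn patient on the week 4, 8 and 12 schedule.

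The primary outcome is "the difference in HAM-D6 score from baseline to end of study at 12 weeks". For patients with a premature endpoint, the section on analysis populations says that "the latest endpoint available will be used with last-observation-carried-forward (LOCF"), and the Statistics section applies this to the primary F-test. A patient with no HAM-D6 rating after baseline is outside the mITT population.

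**The concern.** Stopping the allocated treatment and leaving the study are different events, and the protocol treats them as one. A patient who cannot keep to the arm's treatment, or who meets the suicidality or somatic-illness criterion, may still be willing and able to be rated at week 12. The rule ends their scheduled ratings anyway.

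This matters because the stated aim is the effectiveness of three treatment pathways, and the Study intervention section already lets patients switch, augment or be referred within a pathway. What happens after the first treatment fails is part of the question. Ratings may also go missing unevenly. The ALGO arm follows preset steps while the two usual-care arms leave treatment to the clinician, so inability to follow the treatment may be met more readily in one arm than in another. Allocation is open and the investigator makes the judgement.

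Timing adds to this. The Introduction says that remission often comes four to six weeks after treatment starts, so a rating at an early exit can precede improvement that week 12 would show. This is a rule on data collection, and no later analysis can restore ratings that were not taken.

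**Working it through.** **1. The plan's own figure.** Inputs from the section Power calculation: difference 2.25, SD of change 3.9, two-sided alpha 0.05, power 0.80, three equal arms. For a one-way F-test with arm means 0, 0 and 2.25, the grand mean is 0.75 and the sum of squared deviations is 0.75² + 0.75² + 1.5² = 3.375. With 45 per arm the noncentrality is 45 × 3.375 / 3.9² = 9.99 on 2 and 132 degrees of freedom, which gives power 0.805. Then 45 / 0.80 = 56.25, rounded up to 57, and 3 × 57 = 171. The stated sizes reproduce, and the point does not depend on them.

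**2. The chain in the text.**
- A discontinuation criterion is met.
- The patient is withdrawn from the study, not only from treatment.
- One exit assessment follows if it can be obtained, and no later scheduled visit is stated.
- The exit or previous rating stands in for week 12. With no rating after baseline, the patient is excluded from mITT.

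Nothing is lost if withdrawal falls within the week-12 visit window.

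**3. How many patients at most.** At the planned 20% dropout, 0.20 × 57 = 11.4 per arm and 0.20 × 171 = 34.2 in total. This counts dropout of every kind, including patients who refuse follow-up or cannot be reached, so it is an upper bound on those affected by the rule. The protocol gives no split by reason.

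**4. Size of a shift in the comparison.** Let d be an arm's share of patients with a carried-forward value, and b the mean gap in points between that value and the week-12 score that would have been seen. The arm mean shifts by d × b. The difference between two arms shifts by d₁b₁ − d₀b₀, or (d₁ − d₀) × b if b is the same in both. The protocol gives neither arm-specific dropout nor b, so the values below are assumptions. The formula takes all dropouts as having a rating after baseline.

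| Dropout in the two arms | b = 1 point | b = 3 points |
|---|---|---|
| 20% and 20% | 0 | 0 |
| 25% and 15% | 0.1 (4% of 2.25) | 0.3 (13%) |
| 30% and 10% | 0.2 (9%) | 0.6 (27%) |

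For example, (0.30 − 0.10) × 3 = 0.6, and 0.6 / 2.25 = 27%. With equal dropout and equal b, each arm mean moves by 0.2 to 0.6 points but the difference does not.

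**5. The part that the rule itself causes.** If half of the dropouts in each arm could have been rated at week 12 (an assumption), and they have the same b as the rest, the avoidable part in the last row is 0.5 × 0.2 = 0.1 to 0.5 × 0.6 = 0.3 points, or 4% to 13% of 2.25.

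**The case against.** The protocol is better than a bare withdrawal rule. It gives the exit HAM-D6 first priority and brings forward the next rating for patients who wish to drop out. The carried value is therefore often the score at exit, and close to week 12 for late withdrawals. Mixed models on HAM-D6 are planned as secondary analyses. Reasons for discontinuation and time to discontinuation are compared in the ITT population, so uneven stopping would be visible.

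This stands as mitigation. It does not remove the point: the exit rating is taken only if it can be obtained, it still precedes week 12, and a mixed model has no later ratings to use.

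A reader might infer that the rule removes the patients who do badly on treatment. The criteria do not say that. Non-response and a worsening HAM-D6 are not listed, and all three pathways allow treatment to be changed or added to. Inability to follow the treatment may therefore catch few patients. Of the listed reasons, suicidality and inability to follow treatment are the ones most plausibly tied to how treatment went.

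A reader might also infer that the rule costs 34 week-12 ratings. That figure includes patients who withdraw consent, patients who cannot be contacted (the missed-appointment criterion requires failed contact), and patients never rated after baseline, who are excluded and not carried forward.

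**Conclusion.** The point holds on the wording. The protocol makes every discontinuation criterion an exit from the study, so some patients who could still be rated have no week-12 HAM-D6 by rule, for reasons that may relate to treatment. This could bias the comparison of pathways.

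The documents do not support the claim that it will. A between-arm shift needs unequal dropout or unequal carried-forward error, and the protocol predicts neither. The range runs from zero, when both are equal, to 0.2 to 0.6 points under the assumed 30% versus 10% dropout and 1 to 3 point error. The avoidable part is about half of that if half of the dropouts can be recovered. Confidence is high on the text and limited on the size. The change is advisable because it is cheap and because missed ratings cannot be collected later.

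**What to change.** In the sections Discontinuation criteria and Withdrawal and dropout, define two separate events: stopping the allocated treatment, and leaving the study. Leave the criteria for stopping treatment as they are. State that everyone who has not withdrawn consent to follow-up and can be reached continues the scheduled HAM-D6 and other ratings to week 12, in addition to the exit assessment, and that these ratings are used in the primary analysis. Carrying a value forward would then concern only patients whose week-12 rating is truly unobtainable. Record separately whether a patient stops treatment, declines further ratings, or is lost to contact.

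The cost is amendment wording and some additional virtual ratings by the existing external rater and study staff. Table 1 gives 15 minutes for HAM-D6. The repeated set adds up to 15 (HAM-D6) + 5 (C-SSRS) + 15 (PSP) + 2 (MDI) + 2 (Brief INSPIRE-O) = 39 minutes. A patient misses at most three scheduled ratings, so the ceiling is 34 × 3 = 102 visits, reached only if every dropout left before week 4 and could still be rated. The real number would be lower. The sample size does not change. The amendment helps only patients who have not yet passed week 12.

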### [Completers](#)

Study participants will be defined as completers following the final visit at week 12 after baseline.

## [Recruitment and Information](#)

### [Recruitment of study participants](#)

Recruitment will solely take place from general practices in the North Denmark Region by general practitioners, and participants will be recruited from among their patients.

All eligible patients will be informed that participation in the study is voluntary and a refusal to participate will not affect their treatment in any way. Further, they are informed that, if choosing

to participate, they can withdraw their consent at any given time during the trial. This information will be given by the investigator.

When a general practitioner has found a patient eligible for inclusion into the study, the GP can refer the willing, potential participant to the investigator or study staff for further information regarding the study and for possible participation. An oral acceptance is obtained by the GP, permitting the investigator to contact the potential participant through telephone (pre-screening) to set up a time for the screening visit. The written information about the study will be sent prior to the screening visit but will be discussed during the visit regardless. Inclusion and screening are carried out by the investigator during a physical meeting (screening visit) with the participant. When informed consent has been acquired, baseline interview and ratings can commence. During the screening visit, the participants will receive both the informed consent form as well as oral and written information about the study.

Screening visits for eligibility in the trial as well as virtual meetings can be delegated to a research assistant if deemed competent by the investigator.

### Oral information

The participants will receive oral information about the study in a personal meeting (screening visit) with the investigator or study staff. The oral information will be based on the written information and will be given in a language and level that is comprehensive for the participant. The meeting will be scheduled in a quiet office and the information will be delivered in an uninterrupted and calm environment. The participants will be able to ask questions regarding the study and participation.

Several matters concerning the study will be discussed, such as the study purpose and design, treatment options including the algorithm-based treatment, and advantages and disadvantages for the participants. Further, study discontinuation will be explained, and it will be emphasised that participation in the study is voluntary.

Participants are encouraged to bring a friend or next of kin to the information meeting.

If participants wish, they will be informed by letter about the results of the study, when analysed.

[figure not shown]
### Consent declaration

Study participants will need to sign a consent form at the screening visit and before the first treatment visit. The declaration is in accordance with the recommendations of the Danish National Committee on Health Research Ethics (NVK).

The consent letter will be presented to the possible participant at the screening visit, and it will be up to the individual participant if the consent letter is signed immediately, or if the participant needs time to consider entering the study. The period of consideration will be at least 24 hours and no more than a week.

The consent declaration can be sent in advance before the screening visit, but the letter of consent will be discussed in a personal meeting with the investigator at screening.

## Flowchart of Participant's Course

## Table of Measurements

Week	-2 to -1 Screening	0 Baseline	4	8	12 End of Study	Un-scheduled visit
Meeting form	In person	Virtual meeting	Virtual meeting	Virtual meeting	Virtual meeting	Virtual meeting
Signed Consent Form	X					
Inclusion and exclusion criteria	X					
Oral + written information	X					
Randomisation	X					
Adverse events		X	X	X	X	X
Demographic data	X					
Rating Scales						
HAM-D6		X	X	X	X	X
C-SSRS	X	X	X	X	X	X
PSP		X	X	X	X	
DART		X				
PSE						X*
Self-report forms						
MDI		X	X	X	X	
Brief INSPIRE-O		X	X	X	X	

HAM-D6: The Hamilton Depression Scale, item 6.

C-SSRS: The Columbia-Suicide Severity Rating Scale.

PSE: Present State Examination.

MDI: Major Depression Inventory.

PSP: The Personal and Social Performance Scale.

DART: The Danish Adult Reading Test.

\*In person

All visits and phone calls are scheduled within the defined time frame +/- 3 days. Pre-screening is conducted by a phone call by the investigator or study staff. The written study information will be sent in advance of the screening visit, and if the patient prefers, the letter of consent will also be sent prior to screening. The screening visit is a physical meeting where oral and written information is presented, and written consent can be obtained. Should the patient wish to, they can have at least 24 hours and no more than a week to consider the consent form. A follow-up meeting will be scheduled.

If, during the screening visit, the patient is found to meet all criteria for trial participation, the first treatment visit (baseline visit) will be scheduled within 14 days of the screening. The patient is randomised to treatment at screening.

A virtual baseline meeting is scheduled with the investigator or a competent research assistant. Study visits (virtual meetings) at 4, 8 and 12 weeks, as well as potential telephone calls, are scheduled with the investigator or study staff. Both screening and baseline visits are study related.

Table 1 further visualises the duration of time of each rating scale and interview as well as type of the rating scale, along with the duration of time and type for the different kinds of visits.

	Duration	Type
C-SSRS	1. visit 20 minutes (hereafter 5 minutes)	Rating scale - Interview
PSP	15 minutes	Rating scale - Interview
DART	5 minutes	Rating scale - Interview
HAM-D6	15 minutes	Rating scale - Interview
PSE	60-90 minutes	Semi-structured interview
Brief-INSPIRE-O	2 minutes	Questionnaire – Self-reporting
MDI	2 minutes	Questionnaire – Self-reporting
Screening visit	60 minutes	In person meeting
Baseline meeting	60 minutes	Virtual meeting
Other/un-scheduled visits	30-45 minutes	Virtual meeting

Table 1: Illustrates the duration and type of rating scales and meetings.

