## Aim of the study

The purpose of this study is to investigate the effectiveness of three different treatment pathways for moderate depressive episodes as part of unipolar depressive disorder, through a three-armed, open-label randomised controlled study. Participants will be allocated to one of the three groups in a 1:1:1 ratio.

The three treatment pathways will be as following:

1. Treatment as usual by a general practitioner (TAU-GP).
2. Treatment as usual by a psychologist (TAU-P).
3. An algorithm-based pharmacological treatment by a general practitioner (ALGO).

The primary outcome of the study is to examine whether there is a difference between the three groups. It will be measured by using a F-test from baseline to end of study at 12 weeks, using the Hamilton Depression Scale, 6 item version (HAM-D6).

Additionally, several secondary outcomes will be explored, e.g. the difference in differences (DID) between TAU-GP vs. ALGO, TAU-GP vs. TAU-P and TAU-P vs. ALGO.

The hypothesis is that a tailored algorithm-based treatment regarding patients with depression, treated in general practice, is more effective than treatment as usual (TAU), whether provided by general practitioners (GPs) or psychologists.

Furthermore, a qualitative study will be conducted to investigate the impact of the assigned treatment pathway from the participant's perspectives.

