## Methods and Material

### Study design

To address the aim of the study, an open-label, randomised controlled trial (RCT) will be conducted, as well as a qualitative interview.

Participants will be allocated in a 1:1:1 ratio to either: treatment as usual by a general practitioner (TAU-GP), treatment as usual by a psychologist (TAU-P) in the form of cognitive

behavioural therapy (CBT), or an algorithm-based medical treatment by a general practitioner (ALGO). The duration of the study is up to 14 weeks, with 12 weeks of treatment and up to 2 weeks between screening and baseline. Participants will be evaluated at baseline, 4 weeks, 8 weeks and 12 weeks after baseline, respectively. For all 3 arms, an external rater will carry out the Hamilton Depression Rating Scale (HAM-D) screening.

The study design and duration are illustrated in Figure 1.

[figure not shown]

Figure 1: Study Design (GP: General practitioner. TAU: Treatment as usual. PSE: Present State Examination).

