### Study intervention

In the two treatment as usual arms (TAU-GP and TAU-P), the choice of treatment and the frequency of patient consultations are at the discretion of the general practitioner (GP) and the psychologist. However, the psychologist will utilize cognitive behavioural therapy (CBT) as part of the treatment approach.

In the TAU-GP arm, the GP's can refer patients for psychotherapy, if deemed necessary, after initiation of medication. In the TAU-P arm, the psychologist may request initiation of medication through the general practitioner after psychotherapy, in the form of cognitive behavioural therapy (CBT), has been initiated.

For the algorithm-based treatment arm (ALGO), the GP drafts an individual, algorithm-guided stepped-care plan that merges measurement-based care with pre-set critical decision points (see figure 2). Every 2–4 weeks, validated symptom scores and side-effects are reviewed against evidence-based thresholds. Symptom scale score results are conveyed as “if-then” rules, triggering the next action, e.g. dose optimisation, switch, augmentation, or psychologist referral, as defined at baseline. These structured checkpoints prevent therapeutic drift and ensure the treatment keeps advancing until meaningful improvement is achieved, while still leaving room for clinical judgement and patient preference. The plan is based on the patient’s symptoms, previous treatment history, current clinical guidelines, possible side effects to antidepressants and the general practitioner’s clinical assessment.

The choice of treatment will follow predetermined steps, and the algorithm will include critical decision points (CDPs) at weeks 4, 8 and 12, where treatment efficacy is assessed. This assessment will lead to specific and predetermined adjustments regarding the current treatment (e.g. to continue current treatment or to change choice of treatment from the predefined plan) and in relation to preset “if-then” rules.

[figure not shown]
As a result of lack of tolerability to the current treatment, an earlier switch to an alternative treatment will be possible. In such cases, the algorithm will continue from that point, with a new HAM-D6 measurement conducted four weeks later.

Figure 2 illustrates the baseline measurement of HAM-D6, followed by initial treatment, and subsequent HAM-D6 measurements and treatment decisions at weeks 4 and 8.

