### Randomisation

Patients will be allocated to one of the three arms by randomisation in a 1:1:1 ratio. At least 57 patients are required in each group, including an estimated dropout of 20%, to detect a clinically relevant difference as outlined in the Statistics section.

The randomisation sequence is coded by a single programmer with random block sizes of 3, 6 and 9 participants and with the randomisation sequence stored in REDCap (Research

Electronic Data Capture, Vanderbilt University), thus ensuring inaccessibility to all clinicians using the REDCap module for the randomisation of patients.

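### The baseline HAM-D6 of the primary change score is rated up to 14 days after open-label randomisation, and nothing withholds the allocation until then

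*Protocol*

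**What the plan says.** The Table of Measurements section of the protocol gives the order of events twice. The schedule marks randomisation in the screening column only (week -2 to -1), and the text below it says "The patient is randomised to treatment at screening". In the same schedule the screening cells for HAM-D6, PSP, MDI and Brief INSPIRE-O are empty, and each is first rated at week 0. Of the outcome scales, only C-SSRS is also rated at screening.

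On the gap, that section says "the first treatment visit (baseline visit) will be scheduled within 14 days of the screening". Study design agrees: "with 12 weeks of treatment and up to 2 weeks between screening and baseline".

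Aim of the study calls the trial a "three-armed, open-label randomised controlled study". Study design and Primary outcome measure assign the HAM-D6 to an external rater in all arms, without saying that the rater is masked. The Randomisation section stores the sequence in REDCap, "thus ensuring inaccessibility to all clinicians using the REDCap module for the randomisation of patients".

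Under Primary outcome: "The primary outcome of the study is the difference in HAM-D6 score from baseline to end of study at 12 weeks". The Statistics section tests this change with an F-test across the three arms and with pairwise two-sided t-tests.

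**The concern.** A baseline value is safe to subtract when it cannot depend on the arm. Here the allocation exists for up to two weeks before the baseline is taken. HAM-D6 is an interview, and MDI and Brief INSPIRE-O are self-reports. A participant who knows the arm may therefore answer differently at week 0, even to a masked rater. The arms are easy to tell apart (usual GP care, CBT with a psychologist, algorithm-based medication), so relief or disappointment on learning the allocation is plausible.

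The primary F-test and the pairwise t-tests all start from this rating. If the mean week-0 score in one arm moves because of the allocation and that movement fades by week 12, the fading is counted as treatment effect in that arm. The planned change-score tests cannot separate the two.

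**Working it through.** **Reading the passages together**

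- The order is stated, not inferred: the schedule and the text both put randomisation at screening and the first HAM-D6 at week 0.
- Inaccessibility of the sequence prevents prediction of the next allocation. It does not govern when an allocation already made is disclosed.
- Recruitment of study participants says "When informed consent has been acquired, baseline interview and ratings can commence". This makes consent a precondition for the ratings but does not place them before randomisation.
- Study intervention says "Figure 2 illustrates the baseline measurement of HAM-D6, followed by initial treatment", and the week-0 visit is called the first treatment visit. Week 0 is thus presented as pre-treatment. The issue is knowledge of the allocation, not treatment shown to start before the rating.

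**Inputs** (Power calculation section): difference 2.25 points, SD of change 3.9, two-sided alpha 0.05, power 0.80, 45 per arm, 57 per arm with 20% dropout.

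**The plan's own figure.** For a one-way F-test with one arm differing by d from two equal arms, the noncentrality is λ = n·(2/3)·d²/SD², with 2 and 3n−3 degrees of freedom. For n = 45 and d = 2.25, λ = 45 × 0.6667 × 5.0625 / 15.21 = 9.99, and power is 80.5%. Then 45/0.8 = 56.25, rounded up to 57, and 3 × 57 = 171. The stated sample size reproduces and is not in dispute.

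**Effect of a week-0 shift.** Let one arm's mean shift by b₀ at week 0 because of the allocation, with b₁₂ of it remaining at week 12. The change score is off by d = b₀ − b₁₂ in absolute value. If the shift persists in full, d = 0 and the error rate stays at 5%. The values of d below are assumed, because the protocol gives none.

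| Scenario | 45 per arm | 57 per arm |
|---|---|---|
| No true effect, d = 0.25, F-test | 5.9% | 6.2% |
| No true effect, d = 0.5, F-test | 8.8% | 9.9% |
| No true effect, d = 0.5, pairwise t-test involving that arm | 9.2% | 10.4% |
| True 2.25 in one arm, no shift, F-test | 80.5% | 89.4% |
| True 2.25, d = 0.5 against it (contrast 1.75) | 57.7% | 68.9% |
| True 2.25, d = 0.5 in its favour (contrast 2.75) | 93.8% | 97.8% |

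Worked line: n = 45 and d = 0.5 give λ = 45 × 0.6667 × 0.25 / 15.21 = 0.493, and rejection is 8.8%. For the t-test, the noncentrality is 0.5 / (3.9 × √(2/45)) = 0.608 on 88 degrees of freedom, and rejection is 9.2%.

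**A comparison that does not use week 0.** A shift confined to week 0 cannot enter a comparison of week-12 scores alone. In 20,000 simulated trials at 45 per arm with a 0.5-point week-0 shift, no true effect and baseline-to-week-12 correlations of 0.3, 0.5 and 0.7, the change-score F-test rejected in 8.5%, 8.9% and 8.7%. The week-12-only F-test rejected in 5.2%, 4.8% and 5.0%.

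Its precision depends on that correlation ρ. With equal SDs at both times, the week-12 SD is 3.9/√(2(1−ρ)): 3.30, 3.90 and 5.03 for ρ = 0.3, 0.5 and 0.7. Power for 2.25 points at 45 per arm is then 92.2%, 80.5% and 57.3%. In general the break-even ρ is half the ratio of baseline SD to week-12 SD. If that ratio were 0.7, break-even would be 0.35. At ρ = 0.5 the week-12 SD would be 3.9/√(1 + 0.49 − 0.7) = 4.39, with power 70.1%.

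**The case against.** The strongest reply is that harm needs three links, none documented: the allocation is disclosed before week 0, knowing it moves the rating differently by arm, and the movement has gone by week 12. The figures and the participant flowchart, which might show the order of disclosure and rating, are not available in the text reviewed. The rater is external, and entry requires uncertainty between medication and psychotherapy together with willingness to receive them, which may dampen arm-specific expectations. Randomising at screening may also help to arrange three different pathways, although the protocol does not give that reason.

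Much of this stands as a limit on size. The shift cannot be sized from the protocol, its direction is unknown, and it can inflate a true effect as easily as mask it. A net shift of 0.1 points would matter little (5.1% rejection at 45 per arm). The precision of a week-12-only analysis also depends on unknown SDs and correlation.

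It does not remove the point. The available schedule and text agree with each other, and nothing in them prevents disclosure during up to 14 days of an open-label trial. An external rater does not mask the participant who answers. The exploratory models that include baseline HAM-D6 do not repair it either: with a baseline slope between 0 and 1, adjustment still carries over part of a transient week-0 shift, and these models are not the primary test.

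**Conclusion.** The concern holds. By the protocol's own schedule, the baseline of the primary outcome, and those of PSP, MDI and Brief INSPIRE-O, are measured after randomisation in an open-label trial with no stated masking up to that rating. The order of events is documented. Disclosure before week 0, and any resulting shift, are inferred.

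The bias equals the part of an arm-specific week-0 shift that has gone by week 12. The 0.25- and 0.5-point cases show the mechanism and are not estimates; 0.5 points is 22% of the 2.25-point target (0.5/2.25). The sample size is unaffected. The point should be fixed because the repair is cheap and cannot be made for participants whose week-0 ratings have already been taken with the allocation known.

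**What to change.** **First choice.** State in the Table of Measurements section that the allocation made at screening is withheld from participant and rater until all week-0 ratings (HAM-D6, PSP, MDI, Brief INSPIRE-O, C-SSRS) are saved in REDCap. The cost is one sentence and a REDCap access rule. Staff can still book the pathway in advance if they do not tell the participant or rater; otherwise disclosure and booking come later.

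**Alternative.** Move the REDCap randomisation to the end of the week-0 visit, after those ratings, and correct the randomisation row of the schedule and the sentence that places it at screening. The visit has room: by Table 1, HAM-D6 15 + PSP 15 + C-SSRS 5 + DART 5 + MDI 2 + Brief INSPIRE-O 2 = 44 of 60 minutes, with no duration listed for adverse-event recording. The drawback is that any wait for the allocated provider may fall inside the 12-week window, possibly differently by arm; waiting times are not given.

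**If neither is adopted, or for participants already randomised under the present order.** Add a between-arm comparison of week-12 HAM-D6 without the week-0 value as a sensitivity analysis, noting that it may lose precision.

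None of these needs extra patients, visits or instruments.
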